### 10.6. Severity Assessment

GRADE	Clinical Description of Severity
0	No change from normal or reference (This grade is not included in the Version 4.03 CTCAE document but may be used in certain circumstances.)
1	MILD adverse event
2	MODERATE adverse event
3	SEVERE adverse event
4	LIFE-THREATENING consequences; urgent intervention indicated
5	DEATH RELATED TO adverse event

Note the distinction between the severity and the seriousness of an AE. A severe event is not necessarily an SAE. For example, a headache may be severe (interferes significantly with the subject's usual function) but would not be classified as serious unless it met one of the criteria for SAEs, listed above.

### 10.7. Causality Assessment

The investigator's assessment of causality must be provided for all AEs (serious and non-serious); the investigator must record the causal relationship in the CRF, as appropriate, and report such an assessment in accordance with the SAE reporting requirements if applicable. An investigator's causality assessment is the determination of whether there exists a reasonable possibility that the investigational product caused or contributed to an AE; generally the facts (evidence) or arguments to suggest a causal relationship should be provided. If the investigator does not know whether or not the investigational product caused the event, then the event will be handled as "related to investigational product" for reporting purposes, as defined by the sponsor (see the section on [Reporting Requirements](#)). If the investigator's causality assessment is "unknown but not related to investigational product," this should be clearly documented on study records.

In addition, if the investigator determines that an SAE is associated with study procedures, the investigator must record this causal relationship in the source documents and CRF, as appropriate, and report such an assessment in accordance with the SAE reporting requirements, if applicable.

### 10.8. Exposure During Pregnancy

For both unapproved/unlicensed products and for marketed products, an exposure during pregnancy occurs if:

1. A female becomes, or is found to be, pregnant either while receiving or having been exposed (eg, because of treatment or environmental exposure) to the investigational product; or the female becomes or is found to be pregnant after discontinuing and/or being exposed to the investigational product;

- a. An example of environmental exposure would be a case involving direct contact with a Pfizer product in a pregnant woman (eg, a nurse reports that she is pregnant and has been exposed to chemotherapeutic products).
2. A male has been exposed (eg, because of treatment or environmental exposure) to the investigational product prior to or around the time of conception and/or is exposed during his partner's pregnancy.

If a study subject or study subject's partner becomes or is found to be pregnant during the study subject's treatment with the investigational product, the investigator must submit this information to the Pfizer drug safety unit on an SAE report form and an EDP supplemental form, regardless of whether an SAE has occurred. In addition, the investigator must submit information regarding environmental exposure to a Pfizer product in a pregnant woman (eg, a subject reports that she is pregnant and has been exposed to a cytotoxic product by inhalation or spillage) using the EDP supplemental form. This must be done irrespective of whether an AE has occurred and within 24 hours of awareness of the exposure. The information submitted should include the anticipated date of delivery (see below for information related to termination of pregnancy).

Follow-up is conducted to obtain general information on the pregnancy and its outcome for all EDP reports with an unknown outcome. The investigator will follow the pregnancy until completion (or until pregnancy termination) and notify Pfizer of the outcome as a follow-up to the initial EDP supplemental form. In the case of a live birth, the structural integrity of the neonate can be assessed at the time of birth. In the event of a termination, the reason(s) for termination should be specified and, if clinically possible, the structural integrity of the terminated fetus should be assessed by gross visual inspection (unless preprocedure test findings are conclusive for a congenital anomaly and the findings are reported).

If the outcome of the pregnancy meets the criteria for an SAE (ie, ectopic pregnancy, spontaneous abortion, intrauterine fetal demise, neonatal death, or congenital anomaly [in a live-born baby, a terminated fetus, an intrauterine fetal demise, or a neonatal death]), the investigator should follow the procedures for reporting SAEs.

Additional information about pregnancy outcomes that are reported as SAEs follows:

- Spontaneous abortion includes miscarriage and missed abortion;
- Neonatal deaths that occur within 1 month of birth should be reported, without regard to causality, as SAEs. In addition, infant deaths after 1 month should be reported as SAEs when the investigator assesses the infant death as related or possibly related to exposure to the investigational product.

Additional information regarding the EDP may be requested by the investigator. Further follow-up of birth outcomes will be handled on a case-by-case basis (eg, follow-up on preterm infants to identify developmental delays). In the case of paternal exposure, the investigator will provide the study subject with the Pregnant Partner Release of Information Form to deliver to his partner. The investigator must document in the source documents that the subject was given the Pregnant Partner Release of Information Form to provide to his partner.

### **10.9. Occupational Exposure**

An occupational exposure occurs when, during the performance of job duties, a person (whether a healthcare professional or otherwise) gets in unplanned direct contact with the product, which may or may not lead to the occurrence of an AE.

An occupational exposure is reported to the drug safety unit within 24 hours of the investigator's awareness, using the SAE report form, regardless of whether there is an associated AE/SAE. Since the information does not pertain to a subject enrolled in the study, the information is not reported on a CRF; however, a copy of the completed SAE report form is maintained in the investigator site file.

### **10.10. Withdrawal Due to Adverse Events**

Withdrawal due to AEs should be distinguished from withdrawal due to other causes, according to the definition of AE noted earlier, and recorded on the appropriate AE CRF page.

When a subject withdraws because of an SAE, the SAE must be reported in accordance with the reporting requirements defined below.

### **10.11. Eliciting Adverse Event Information**

The investigator is to report all directly observed AEs and all AEs spontaneously reported by the study subject/parent(s)/legal guardian/legally acceptable representative. In addition, each study subject/parent(s)/legal guardian/legally acceptable representative will be questioned about AEs.

### **10.12. Reporting Requirements**

Each AE is to be assessed to determine if it meets the criteria for SAEs. If an SAE occurs, expedited reporting will follow local and international regulations, as appropriate.

#### **10.12.1. Serious Adverse Event Reporting Requirements**

If an SAE occurs, Pfizer is to be notified within 24 hours of investigator awareness of the event.

In particular, if the SAE is fatal or life-threatening, notification to Pfizer must be made immediately, irrespective of the extent of available AE information. This time frame also applies to additional new information (follow-up) on previously forwarded SAE reports as well as to the initial and follow-up reporting of EDP, exposure via breastfeeding, and occupational exposure cases.

In the rare event that the investigator does not become aware of the occurrence of an SAE immediately (eg, if an outpatient study subject initially seeks treatment elsewhere), the investigator is to report the event within 24 hours after learning of it and document the time of his or her first awareness of the AE.

For all SAEs, the investigator is obligated to pursue and provide information to Pfizer in accordance with the time frames for reporting specified above. In addition, an investigator may be requested by Pfizer to obtain specific additional follow-up information in an expedited fashion. This information collected for SAEs is more detailed than that captured

on the AE CRF. In general, this will include a description of the AE in sufficient detail to allow for a complete medical assessment of the case and independent determination of possible causality.

Information on other possible causes of the event, such as concomitant medications, vaccines, and/or illnesses, must be provided. In the case of a subject death, a summary of available autopsy findings must be submitted as soon as possible to Pfizer or its designated representative.

#### **10.12.2. Nonserious Adverse Event Reporting Requirements**

All AEs will be reported on the AE page(s) of the CRF. It should be noted that the form for collection of SAE information is not the same as the AE CRF. Where the same data are collected, the forms must be completed in a consistent manner. For example, the same AE term should be used on both forms. AEs should be reported using concise medical terminology on the CRFs as well as on the form for collection of SAE information.

#### **10.12.3. Sponsor's Reporting Requirements to Regulatory Authorities**

AE reporting, including suspected unexpected serious adverse reactions, will be carried out in accordance with applicable local regulations.

#### **10.13. Breaking the Blind**

This is an open-label study and breaking the blind is not applicable.

### **11. GUIDANCE TO THE INVESTIGATOR**

**Risk/Benefit Statement** FRAGMIN (dalteparin sodium) was first approved for marketed use in 1985 and there has been extensive post-marketing and clinical trial exposure. However, the safety and effectiveness of FRAGMIN in the pediatric population has not been established. This is primarily a study of the safety and pharmacodynamics of FRAGMIN in children with or without cancer and venous thromboembolism. As with any medication, it must be emphasized that serious adverse events, previously identified or not, may occur. Subjects participating in this study cannot be guaranteed a clinical benefit from the administration of the test drug. Thus, for each subject, the possibility of a positive therapeutic effect and their contribution to the scientific understanding of the long term safety of FRAGMIN are the only possible benefits.

### **12. STATISTICAL METHODS**

#### **12.1. Determination of Sample Size**

Subjects, with or without a diagnosis of various cancers within 6 months of the Screening Visit and requiring anticoagulation for the treatment and secondary prophylaxis of VTE, will be enrolled into the following five age groups:

- 0 to < 8 Weeks;
- $\geq$  8 Weeks to < 2 Years;
- $\geq$  2 Years to < 8 Years;
- $\geq$  8 Years to < 12 Years;

- $\geq 12$  Years to  $< 19$  Years.

Target enrollment is 50 subjects. A sample size of 50 subjects is sufficient to estimate Anti-Xa clearance and  $V_d$  of dalteparin. Enrollment will continue until 50 subjects have viable PD profiles after treatment doses of dalteparin.

The sample size was determined based on historical data and a population pharmacokinetic (PK)/PD model, evaluation of the effect of sample scheme and sample size per age stratum on the bias and precision of key PK/PD parameters, after evaluation of total N of 10, 20, 30, 40 and 50 (2, 4, 6, 8, 10 per age stratum as available) and evaluation of single and 2-point sample densities and impact of randomization across strata with 100 trial simulations per design examined. In addition, blood sampling density was also considered after the subject sample size was determined. Single-point sampling designs yielded unacceptable bias in total body clearance of the drug (CL) and/or  $V_d$ ; confounding of effects if blocked within stratum. Double sampling at 3, 8 and 5, 12 hours post-dose performs more efficiently. Therefore, randomized two-sample design per each subject was also determined.

See [Appendix 3](#) for additional information regarding the trial simulation strategy.

## **12.2. PD Phase Plasma Sampling Randomization Plan**

Enrolled subjects who achieve the target therapeutic Anti-Xa level in the Dose Adjustment Phase will advance to the PD Phase. Subjects will be randomized (at Baseline) to two different plasma sampling schemes (1 to 3 h and 5 to 8 h, or 3 to 5 h and 8 to 12 h) in the PD Phase with a ratio of 1:1 in each age group and the randomization will be blocked and stratified by age group via the electronic system, IMPALA. Randomization will continue until 50 subjects have viable PD Phase profiles.

## **12.3. Statistical Plan**

### **12.3.1. Statistical Methodology**

All statistical analyses will be performed using SAS® (Version 9.1 or higher), and will be assessed at the two-sided 0.05 level. Mean, standard deviation, median, minimum and maximum will be summarized for continuous variables. Frequency and percentage will be summarized for categorical variables. Ninety-five percent (95%) confidence intervals will be provided for primary and selected secondary safety endpoints. Paired t-tests will be performed for the changes from baseline for selected continuous variables. Time to event will be described by using the Kaplan-Meier method. In addition, the Cox Proportional Hazard Regression model will be employed to assess the hazard ratio of the event with prognostic factors.

### **12.3.2. Definition of Study Populations for Analysis**

There will be two analysis populations defined in the study.

- Safety Population: Subjects who receive at least one treatment of dalteparin. All safety analysis will be based on this population;
- Pharmacodynamic Population: Subjects in the Safety Population who achieve therapeutic range of anti-Xa during Dose Adjustment Phase. This population will be the primary analysis population for PD and efficacy analysis.

### **12.3.3. Analysis of Baseline and Demographic Variables**

Demographic and pretreatment characteristics for the safety population will be summarized for all subjects and by age group using descriptive statistics including number of subjects, mean, standard deviation, median and range for continuous variables; and the frequency and percent for categorical variables.

### **12.3.4. Analysis of Pharmacodynamic Variables**

All PD variables will be analyzed within the PD population.

The primary study analysis will be a PD evaluation of dalteparin based on Anti-Xa levels using a population PD analysis methodology. Due to the sparse plasma sampling strategy, population PD analyses will be explored. The PD effect (Anti-Xa level) is used as a surrogate PK of dalteparin for the time course of drug exposure. The population PD analysis may also be named as a population PK analysis. Details of the Population PD analysis will be described in a separate population PD modeling analysis plan document and results will be presented in a separate population PD report.

The secondary PD analyses will include the proportion of children achieving an Anti-Xa therapeutic range of 0.5 to 1.0 IU/mL at 4 hours  $\pm$  1 hour post-dose during the Dose Adjustment Phase (up to 7 days) and the proportion of subjects who remain within therapeutic range over the Follow-Up Phase (Visits 5, 6 and 7). These analyses will be descriptively summarized for all subjects and by age groups.

The final dose of dalteparin given to a subject during the Dose Adjustment Phase of the study will be considered the maintenance therapeutic dose (ie, the dose achieving an Anti-Xa level of 0.5 to 1.0 IU/mL at 4 hours  $\pm$  1 hour post-dose). The time to achieve the target range is defined as the number of days from the first dose to the final dose that achieves the target Anti-Xa level. The maintenance dose, time to achieve the target range, and number of dose adjustments during the Dose Adjustment Phase will be summarized by age group using summary statistics.

Aggregate PD profiles (curves of Anti-Xa level versus hours after dosing time) and summary measures will be calculated using combined data for all subjects within a given age group.

Additionally, for each age group, the percentage of Anti-Xa levels measured 4 hours post-dose  $\pm$  1 hour post-dose that are outside the target range will be calculated during the Follow-up Phase of the study.

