#### 4. STUDY OBJECTIVES AND ENDPOINTS

The primary objective of this study is to:

- To determine the PD profiles for treatment doses of dalteparin in pediatric subjects of different ages with or without cancer and VTE, using Anti-Xa levels and a population PD analysis methodology;
- To determine the median dose (IU/kg) required to achieve therapeutic Anti-Xa levels (0.5-1.0 IU/mL) based on subject age and weight.

Secondary objectives will be:

- To assess the proportion of major bleeding events during dalteparin treatment;
- To assess the proportion of minor bleeding events during dalteparin treatment;
- To explore the proportion of objectively documented new or progressive symptomatic VTE during dalteparin treatment;
- To explore the relationships of recurrent VTE and major bleeding events with anti-Xa levels, if data permits;
- To explore the proportions of subjects with progression, regression, resolution or no change in the qualifying VTE during dalteparin treatment;
- To describe the overall safety profile of dalteparin in pediatric subjects of different ages with or without cancer and VTE.
- To assess the proportion of subjects achieving an anti-Xa therapeutic range of 0.5 to 1.0 IU/mL during the Dose Adjustment Phase.

Primary Endpoints:

- Determine the median dose of dalteparin (IU/kg) associated with the achievement of the therapeutic Anti-Xa level (0.5-1.0 IU/mL) among subjects that achieved their therapeutic Anti-Xa level during the dose adjustment phase, for each age cohort group;
- Anti-Xa activity versus time profile following dalteparin treatment will be explored using a population PD analysis methodology. Population PD parameters such as clearance, volume of distribution, absorption rate constant will be estimated based on Anti-Xa levels collected during dose adjustment phase, PD phase and follow-up phase. Age and other relevant covariates will be explored in the population PD analysis.

Secondary Endpoints:

- Proportion of subjects achieving an Anti-Xa therapeutic range of 0.5 to 1.0 IU/mL during the Dose Adjustment Phase (up to 7 days);
- Proportion of subjects with objectively documented, new or progressive symptomatic VTE during dalteparin treatment utilizing the same objective technique performed at Baseline;
- Time to first episode of symptomatic recurrent VTE during dalteparin treatment;

[figure not shown]

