### **3. ENDPOINTS AND BASELINE VARIABLES: DEFINATIONS AND CONVENTIONS**

#### **3.1. PD Endpoint(s)**

##### **3.1.1. Primary PD Endpoints**

- Anti-Xa activity versus time profile following dalteparin treatment in pediatric subjects of different ages with VTE.

Note: This is beyond the scope of the SAP and it will be detailed in a separated population modeling analysis plan (PMAP-EQDD-A630c-DP4-560).

- Median dose required per age group to achieve an anti-Xa level of 0.5 to 1.0 IU/mL during the dose adjustment phase.

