### **6.1. Endpoint(s)**

#### **6.1.1. PD Endpoints**

Unless otherwise noted, all PD endpoints will be analyzed within the PD population.

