#### **6.1.1.2. Secondary PD Endpoints**

- Proportion of subjects achieving an anti-Xa therapeutic range of 0.5 to 1.0 IU/mL during the Dose Adjustment Phase.

The count and proportion will be summarized overall and by each age group within the safety population, along with the two-sided exact 95% CI.

- Proportion of subjects who remain within therapeutic range at each visit during the follow up phase (Visit 5, Visit 6 and Visit 7).

The count and proportion will be summarized overall and by each age group, along with the two-sided exact 95% CI.

- The percentage of anti-Xa levels measured 4 hours post dose  $\pm 1$  hour that are outside the target range will be calculated at each visit during the follow up phase of study (Visit 5, Visit 6 and Visit 7).

The count and percentage will be summarized overall and by each age group, along with the two-sided exact 95% CI.

- The maintenance dose, time to achieve the target range, and number of dose adjustment during dose adjustment phase.

The maintenance dose, time to achieve the target range, and number of dose adjustments will be summarized overall and by each age group.

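### As the protocol reads, the primary population PD model leaves out children who never reached the anti-Xa range, although their timed dose-adjustment levels exist

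*Protocol*

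**What the plan says.** Protocol 12.3.4 opens with the rule "All PD variables will be analyzed within the PD population" and continues: "The primary study analysis will be a PD evaluation of dalteparin based on Anti-Xa levels using a population PD analysis methodology". Section 12.3.2 defines the population as "Subjects in the Safety Population who achieve therapeutic range of anti-Xa during Dose Adjustment Phase" and makes it the main set for PD and efficacy.

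Protocol section 4 lists two primary endpoints. The median dose is expressly confined to children who reached their level. The population parameters carry no such limit and "will be estimated based on Anti-Xa levels collected during dose adjustment phase, PD phase and follow-up phase".

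The model's specification is placed elsewhere. The protocol says "Details of the Population PD analysis will be described in a separate population PD modeling analysis plan document", and SAP 3.1.1 says "This is beyond the scope of the SAP and it will be detailed in a separated population modeling analysis plan". SAP 6.1.1 still sets a default: "Unless otherwise noted, all PD endpoints will be analyzed within the PD population". It lists this endpoint beneath that default, in 6.1.1.1, with a pointer to the modelling plan. The one PD endpoint given a different set is the proportion reaching range, in 6.1.1.2: "The count and proportion will be summarized overall and by each age group within the safety population".

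A child still out of range at the end of the 7 days is withdrawn (protocol 7 and 8.2). Children who do not complete the PD Phase are replaced until 50 have usable data (6.3.2).

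**The concern.** Entry to the PD population depends on the response that the model describes. A child who misses the range has been dosed and sampled. Dose-adjustment samples go to the central as well as the local laboratory (Table 1, footnote 5), and actual dose and draw times are recorded (5.2, 9.1.8). Because the child is then withdrawn, those samples are all the model could ever have from that child. A mixed-effects model can use them.

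Leaving them out trims the sample on exposure, which tends to understate between-child variability. Where the starting level is low for an age group, it also lowers that group's estimated clearance. Replacement does not repair this, because replacements pass through the same filter. The study is meant to support dosing recommendations by age (5.1), so a distortion that can differ between age groups matters.

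**Working it through.** **The plan's own figures.** The arithmetic is consistent: 5 strata × 10 = 50 subjects, and 4 × 2 × 100 = 800 simulated trials in Appendix 3. The claim that 50 suffices cannot be reproduced, because the model parameters, variances and precision criterion are not given. Neither document states an expected share of non-achievers or a bias from excluding them. The size below is therefore a simulation on stated assumptions.

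**Inputs from the documents.** Starting doses are 100, 125 or 150 IU/kg, steps are 25 IU/kg and the window is 0.5–1.0 IU/mL. At most six adjustments are allowed up to Day 7. Dosing is 12-hourly, with sampling 4 h after the first, second or third dose. The only spread figure is the 129 ± 43 IU/kg treatment dose in the cited 48-child dalteparin series (3.2): CV = 43/129 = 0.333, log-SD = √ln(1 + 0.333²) = 0.325. That series used once-daily dosing, so it is only a proxy for between-child spread.

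**Assumptions.** Level is proportional to dose/clearance. Clearance is lognormal with CV 40–60% (log-SD 0.385–0.555), and residual error is 20%. The typical level at the starting dose is either 0.75 (mid-range) or 0.41–0.53.

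**How many adjustments fit.** If sampling always waits for the third dose and the result is back before the next dose, the first sample falls at 24 + 4 = 28 h. Each adjustment then takes 36 h, so samples follow at 64, 100 and 136 h, and the next would fall at 172 h, beyond 168 h. Three adjustments can be tested. One next-day repeat still leaves three (136 + 24 = 160 h). Two repeats leave two (184 h). Sampling after the first dose leaves room for all six.

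**Reach of the titration.** From 125 IU/kg, six steps up give 275 (ratio 2.2) and three give 200 (ratio 1.6). Downward, the dose can fall to 25 (ratio 0.20). Ignoring noise, a child with c times the typical clearance can be brought up to 0.5 if c ≤ m × ratio/0.5, where m is the typical starting level:
- m = 0.75, six steps: c ≤ 0.75 × 2.2/0.5 = 3.30.
- m = 0.41, three steps: c ≤ 0.41 × 1.6/0.5 = 1.31.

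On the low side with six steps and m = 0.75, a child is lost only if c < 0.75 × 0.20/1.0 = 0.15.

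**Achievers compared with all treated** (start 125 IU/kg, 400,000 children per scenario, CV 40–60%):

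| Typical starting level | Adjustments tested | Excluded | Geometric-mean clearance | SD of log-clearance |
|---|---|---|---|---|
| 0.75 | 6 | 0.1–1.4% | at most about 1.4% too low | 0.4–4% too small |
| 0.41–0.53 | 2–3 | 8–37% | 5–26% too low | 12–33% too small |

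Repeat runs move the upper ends by up to about one percentage point. In the second row the excluded children have about 1.5–2.1 times the typical clearance.

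**Fitted models.** A random-intercept model was fitted by maximum likelihood (12,000 children per scenario, start 125 IU/kg). Achievers were given five further samples, two in the PD Phase and three in follow-up. Results for the achievers-only fit:

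| Starting level | Adjustments | Log-SD | Excluded | Clearance bias | SD ratio |
|---|---|---|---|---|---|
| 0.75 | 6 | 0.325 | 0.04% | −0.5% | 0.99 |
| 0.40 | 6 | 0.325 | 3.4% | −2.2% | 0.93 |
| 0.40 | 3 | 0.325 | 19% | −10% | 0.79 |
| 0.75 | 6 | 0.7 | 4.0% | −4.2% | 0.90 |
| 0.40 | 3 | 0.7 | 34% | −30% | 0.66 |

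Fitted to all treated children, the same model recovered clearance within about 1% and the SD within about 2% in every scenario. For scale, the sampling SE of mean log-clearance at n = 50 is 0.325/√50 = 0.046, and Appendix 3 considers a 30% clearance difference from adults.

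**By starting dose.** At the same typical level (0.41), CV 40% and three adjustments, the clearance bias is about −10%, −12% and −14% for starts of 100, 125 and 150 IU/kg. The fixed step is a smaller fraction of a larger start.

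**The case against.** The strongest reply is that the operative analysis set is in a document not supplied. Both the protocol and the SAP defer the model to it, and SAP 3.1.1 puts this endpoint outside its own scope, so SAP 6.1.1 is weak as a second source. The opening rule of 12.3.4 also cannot be literal for everything beneath it: it would make the proportion reaching range 100% by definition, which SAP 6.1.1.2 avoids by using the safety population. Section 4 itself suggests wider data use. A reader might infer that non-achievers' data will certainly be discarded. The documents do not establish that; they show what the protocol text says. This part of the reply stands. It does not remove the point, because a modelling plan with a wider set would contradict 12.3.4 and the texts would still need aligning.

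The second reply is that the large figures stack assumptions. Six adjustments are permitted, daily levels are described (7, 9.1.8), protocol 8.4 reports that similar dosing gave levels in range, and the one documented spread (CV 33%) is below the 40–60% assumed. With that spread, mid-range starting levels and six adjustments, the bias is far below the sampling error. This stands for that case. Slow sampling is nevertheless allowed by the protocol, and low starting levels in some age group cannot be excluded from the documents.

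**Conclusion.** The concern holds as a defect of the protocol text, with an effect that may be negligible or material. As written, 12.3.4 with 12.3.2 selects the primary model's sample on the modelled response and conflicts with section 4. The effect is negligible when starting levels are mid-range and six adjustments are used. It becomes material when starting levels are low and few adjustments can be tested. Between age groups the bias varies only modestly at equal starting level; larger differences would need starting levels that differ by age.

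A reader might infer that both the highest- and the lowest-clearance children are removed. The titration rule does not support this. Under six adjustments the low-clearance loss was at most 0.6% in every scenario, because the dose can fall to 25 IU/kg. It reached 5.3% only with three adjustments, a mid-range start and log-SD 0.7 (CV about 80%). Nor does failure identify clearance alone: selection acts on the 4-hour level, which also reflects absorption, volume and assay noise, and some children stop for other reasons.

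Confidence is high for the protocol wording and medium for the actual bias, which rests on assumed spread, residual error, starting level and proportionality.

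**What to change.** In protocol 12.3.4, and in matching words in SAP 6.1.1 and the modelling plan, state that the population PD model uses every Safety Population child with at least one evaluable post-dose anti-Xa level and recorded dose and draw times, whether or not the range was reached. Keep the PD population for the median-dose endpoint, and report the achievers-only fit of the model as a sensitivity analysis.

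The cost is about one sentence in each document and slightly more modelling work. It needs no extra samples or patients and touches no dosing or withdrawal rule. Reported between-child variability may come out somewhat larger.
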